- Platelets  $\geq$ 50,000 cells/mm^3 for patients who have bone marrow plasmacytosis  $<$ 50% or  $\geq$ 30,000 cells/mm^3 for patients who have bone marrow plasmacytosis of  $\geq$ 50%
- Calculated or measured creatinine clearance  $\geq$ 30 ml/min (see Appendix V)
- Total bilirubin  $\leq$ 1.5 x upper limit of normal (ULN) unless due to Gilbert's syndrome.
- Aspartate aminotransferase (AST)/SGOT and alanine aminotransferase (ALT)/SGPT  $\leq$ 3 x ULN
- PT/INR  $\leq$ 1.5 X ULN

3.18 Provide informed written consent.

3.19a Willing to return to enrolling institution for follow-up (during the Active Monitoring Phase of the study).

3.19b Persons able to become pregnant must be willing to adhere to the scheduled pregnancy testing as required in the REVLIMID REMS™ program.

3.19c Willing to be registered into the mandatory REVLIMID REMS™ program, and willing and able to comply with the requirements of the REVLIMID REMS™ program.

3.19d Ability to complete study-related (QoL, pill diary) questionnaire(s) by themselves or with assistance.

3.19e Willing to provide bone marrow aspirate and core, and blood samples for correlative research purposes (see Sections 6.31, 14.0).

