## 8.3 Lenalidomide Dose Modifications

→ → Use the NCI Common Terminology Criteria for Adverse Events (CTCAE) version 4.0\*  
unless otherwise specified ← ←

CTCAE System/Organ/Class (SOC)	ADVERSE EVENT	AGENT	ACTION**
Investigations	Platelet count decreased Grade 4	Lenalidomide	
*Omit dose until AE has resolved to Grade 1 or better
 
 
• Follow CBC weekly
 
• If thrombocytopenia <math><30,000/\text{mm}^3</math> recurs, reduce dose by one dose level (by 5 mg) and continue therapy when platelet count <math>\geq 30,000/\text{mm}^3</math>
 
 
If, after lenalidomide has been omitted, and the AE does not return to <math>\leq</math>Grade 1 within 4 weeks, then the patient must be removed from protocol treatment and proceed to Event Monitoring

	Neutrophil count decreased Grade 4		
*Omit dose until AE has resolved to Grade 1 or better
 
 
• Follow CBC weekly
 
* If neutropenia has resolved to <math>\leq</math>Grade 2, resume dose at one level lower
 
*If, after lenalidomide has been omitted, and the AE does not return to <math>\leq</math>Grade 1 within 4 weeks, then the patient must be removed from protocol treatment and proceed to Event Monitoring
 

CTCAE System/Organ/Class (SOC)	ADVERSE EVENT	AGENT	ACTION**
Blood and lymphatic system disorders	Anemia Grade 4		
 
*Omit dose until AE has resolved to Grade 2 or better
 
• Follow CBC weekly
 
* If anemia has resolved to <math>\leq</math>Grade 2, resume dose at one level lower
 
*If, after lenalidomide has been omitted, and the AE does not return to <math>\leq</math>Grade 2 within 4 weeks, then the patient must be removed from protocol treatment and proceed to Event Monitoring
 

	Febrile neutropenia $\geq$ Grade 3		
 
• Omit dose and follow CBC weekly
 
• If neutropenia has resolved to <math>\leq</math>Grade 2, resume dose at same level with GCSF support (See Section 9.7)
 

Cardiac disorders	Sinus bradycardia/other cardiac arrhythmia Grade 2	Lenalidomide	
 
Omit dose and follow at least weekly until resolution
 
• If AE resolves to <math>\leq</math>Grade 1, reduce dose by one dose level (by 5mg) and continue therapy
 

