	$\geq$ Grade 3		
 
• Discontinue study treatment and go to event monitoring
 

Vascular disorders	Thromboembolic event $\geq$ Grade 3		
 
• Omit dose and start anticoagulation; restart at investigator's discretion (maintain dose level)
 

Immune system disorders	Allergic reaction Grade 2-3		
 
• Omit dose and follow at least weekly until resolution
 
• If AE resolves to <math>\leq</math>Grade 1, reduce dose by 5 mg and continue therapy
 

	Anaphylaxis Grade 4		
 
• Discontinue study treatment and go to event monitoring
 

Skin and subcutaneous tissue disorders	Erythema multiforme $\geq$ Grade 3		Discontinue study treatment and go to event monitoring
	Skin ulceration $\geq$ Grade 2		Discontinue study treatment and go to event monitoring
	Other: Non-blistering rash Grade 3		
 
• If Grade 3 omit dose and follow weekly until resolution
 
• If AE resolves to <math>\leq</math>Grade 2 continue therapy
 

	Other: Non-blistering rash Grade 4		
 
• Discontinue study treatment and go to event monitoring
 

Other AEs	Non-hematologic AE assessed as related to lenalidomide $\geq$ Grade 3		
 
• Omit dose and follow at least weekly until resolution
 
• If the AE resolves to <math>\leq</math>Grade 2, implement one dose reduction step and continue therapy (per Table 8.2)
 

\* Located at [http://ctep.cancer.gov/protocolDevelopment/electronic\\_applications.ctc.htm](http://ctep.cancer.gov/protocolDevelopment/electronic_applications.ctc.htm)

\*\* Use the following to describe actions in the Action column:

- Omit = The current dose(s) for the specified drug(s) during a cycle is skipped. The patient does not make up the omitted dose(s) at a later time
- Hold/Delay = The current dose(s) of all drugs during a cycle is delayed. The patient does make up the delayed dose(s) when the patient meets the protocol criteria to restart drugs.
- Discontinue = The specified drug(s) are totally stopped.

If lenalidomide has been omitted and the toxicity does not return to  $\leq$ Grade 2 within 28 days, the patient must be removed from protocol treatment and proceed to Event Monitoring.

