## 8.5 Ibrutinib Dose Modifications

→ → Use the NCI Common Terminology Criteria for Adverse Events (CTCAE) version 4.0\* unless otherwise specified ← ←

CTCAE System/Organ/Class (SOC)	ADVERSE EVENT	AGENT	ACTION**
Investigations	Neutrophil count decreased Grade 4 lasting >7 days	Ibrutinib	Omit ibrutinib** until recovery to Grade ≤1 or baseline May restart at same dose for first occurrence Each subsequent occurrence may restart at next lower dose after recovery to Grade ≤1 or baseline If AE occurs at lowest dose discontinue treatment and go to event monitoring
	Platelet count decreased Grade ≥3		
Blood and lymphatic system disorders	Febrile neutropenia ≥Grade 3	Ibrutinib	Omit ibrutinib** until fever resolves and ANC ≥1000/µL, then resume ibrutinib at the previous dose
Gastrointestinal disorders	Nausea ≥Grade 3 (if persistent despite optimal antiemetic therapy) Vomiting ≥Grade 3 (if persistent despite optimal antiemetic therapy) Diarrhea ≥Grade 3 (if persistent despite optimal anti-diarrheal therapy)	Ibrutinib	Omit ibrutinib** until recovery to Grade ≤1 or baseline May restart at same dose for first occurrence Each subsequent occurrence may restart at next lower dose after recovery to Grade ≤1 or baseline If AE occurs at lowest dose discontinue treatment and go to event monitoring
Other (Non-hematologic)****	Any other Grade 4 AE or any unmanageable Grade 3 AE	Ibrutinib	Omit ibrutinib** until recovery to Grade ≤1 or baseline May restart at same dose for first occurrence Each subsequent occurrence may restart at next lower dose after recovery to Grade ≤1 or baseline If AE occurs at lowest dose discontinue treatment and go to event monitoring

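### Section 8.3 sets inconsistent recovery and removal thresholds for lenalidomide after Grade 4 thrombocytopenia, and none allows for the low baseline counts that 3.17 admits

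*Combined protocol and SAP*

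**What the plan says.** **Lenalidomide, 8.3, Grade 4 platelet row.** The restart instruction is "Omit dose until AE has resolved to Grade 1 or better". If Grade 1 is not regained "within 4 weeks, then the patient must be removed from protocol treatment and proceed to Event Monitoring". For a recurrence below 30,000/mm³ the same row says to "reduce dose by one dose level (by 5 mg) and continue therapy when platelet count" is at least 30,000/mm³. No line of the row mentions the patient's baseline.

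**Lenalidomide, 8.3, paragraph below the table.** This opens "If lenalidomide has been omitted and the toxicity does not return to" and then names Grade 2 or better within 28 days as the condition for staying on protocol treatment.

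**Eligibility, 3.17.** The platelet floors are "50,000 cells/mm 3 for patients who have bone marrow plasmacytosis" under 50%, and "30,000 cells/mm 3 for patients who have bone marrow plasmacytosis of" 50% or more.

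**Where baseline is accepted.** For ibrutinib, 8.5 withholds drug "until recovery to Grade ≤1 or baseline". In the table as extracted, the platelet entry (Grade 3 or worse) appears to share that action cell with the neutrophil entry. Section 7.31 accepts baseline in the same way for a Phase I dose-limiting toxicity.

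**How binding the tables are.** Section 8.0 makes them strict for the first cycle of the three-drug combination, excludes the MTD-finding period, and treats them as guidelines afterwards. Separately, 8.1f bars any omission of lenalidomide or ibrutinib beyond 28 days and sends the patient to event monitoring.

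**The concern.** Two problems meet in one row. First, a site managing Grade 4 thrombocytopenia finds different answers within 8.3 on when lenalidomide may resume and when the patient leaves treatment. Second, the strictest of those answers asks for a platelet grade that some patients did not have when they were enrolled.

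At stake is whether a patient who is back at an eligible baseline stays on protocol treatment, and whether that depends on which line the site reads. The primary endpoint in 16.11 and 16.411 needs response on two consecutive evaluations, so a patient taken off before the second one may lose a response that would otherwise have counted. The Phase II cut-offs are 11 of 15 and 26 of 34.

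**Working it through.** No figure in the plan is in dispute, so the check sets the rules side by side and then compares them with the entry limits.

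**Step 1: the rules for one event.**

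| Place | Applies to | Recovery needed | Baseline accepted |
|---|---|---|---|
| 8.3 platelet row, restart | lenalidomide, Grade 4 platelets | Grade 1 | no |
| 8.3 platelet row, removal | same, at 4 weeks | Grade 1 | no |
| 8.3 platelet row, recurrence bullet | platelets below 30,000/mm³ again | 30,000/mm³ | not mentioned |
| 8.3 closing paragraph | any toxicity with lenalidomide omitted, at 28 days | Grade 2 | no |
| 8.1f | omission of lenalidomide or ibrutinib, any cause | none; removal after more than 28 days | no |
| 7.31 | Phase I dose-limiting toxicity | Grade 1 | yes |
| 8.5 | ibrutinib, platelets Grade 3 or worse | Grade 1 | yes |

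Four weeks and 28 days are the same interval, so the row and the closing paragraph differ only in grade. A patient at Grade 2 on day 28 is removed by the row and not by the closing paragraph. The row's removal sentence is not limited to a first event, so after a recurrence it also conflicts with the bullet beside it.

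**Step 2: the closing paragraph does not settle it.** A patient at Grade 2 escapes removal under that paragraph but still fails the row's restart condition. Lenalidomide stays off, and once the omission passes 28 days 8.1f requires removal. The exception in the notes to 8.5 covers only delays unrelated to treatment toxicity.

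**Step 3: eligible baselines against Grade 1.** The documents name CTCAE v4.0 but do not print its platelet cut-points, so the lower bound of Grade 1 is an assumption and is shown as a range.

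| Assumed Grade 1 lower bound (/mm³) | Eligible baselines worse than Grade 1, marrow 50% or more | Same, marrow under 50% |
|---|---|---|
| 50,000 | 30,000–49,999 | none |
| 60,000 | 30,000–59,999 | 50,000–59,999 |
| 75,000 | 30,000–74,999 | 50,000–74,999 |

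For any bound above 30,000/mm³ the set is not empty. The plan itself points that way: the recurrence bullet treats a count below 30,000/mm³ as the Grade 4 problem returning, so a patient enrolled at the 30,000/mm³ floor is unlikely to be at Grade 1.

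If Grade 2 ends at 50,000/mm³ (also an assumption), the closing paragraph would keep a patient who returns to a baseline of 50,000–74,999 and remove one who returns to 30,000–49,999.

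**Step 4: when the row is strict.** In Phase II lenalidomide starts in Cycle 2, so that is the first combination cycle and the period in which 8.0 requires the table to be followed strictly. In Phase I Cycle 1, Grade 4 platelets are a dose-limiting toxicity under 7.32 and 7.31 applies, with its baseline alternative.

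**Step 5: link to the endpoint.** Cycle 2 Day 1 is study day 29. A Grade 4 event on that day, with 28 days of omission, leads to removal at about day 29 + 28 = 57. Section 4.1 schedules disease tests on Day 1 of each cycle, hence at about days 29 and 57, and again at end of treatment. Some responses could be confirmed by then; slower ones could not. For scale, one patient is 1/34 = 2.9 percentage points of the final Phase II rate.

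**The case against.** The best defence has four parts.

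- **The tables soften.** After the first combination cycle they are guidelines, so an investigator could restart before day 28. That is true, but it leaves the strict cycle untouched, the row still says removal is mandatory, and 8.1f sets its own limit. Guideline status also does not tell a site which threshold to use.
- **The lines may have separate scopes.** The 30,000/mm³ bullet concerns a recurrence, and the closing paragraph could be a default for rows without a removal rule of their own. This is a reasonable reading, but the text does not state it.
- **Different drugs may carry different thresholds.** Section 15.27 lists a boxed warning for thrombocytopenia with lenalidomide, so a stricter lenalidomide rule could be deliberate. This stands: a difference between 8.3 and 8.5 is not a contradiction in itself, and the baseline clause in 8.5 does not override 8.3. It shows only that the plan uses the idea of baseline elsewhere and is silent on it here.
- **Failure is not automatic.** Agents judged unrelated to the event may continue under 8.1e. A response already confirmed still counts. Footnote a of Table 11.5 allows the two assessments at any time before new therapy, and 16.411 says at any time, although 16.11 says during treatment. This stands too.

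A reader might infer that eligible patients with low counts are forced off treatment and scored as failures. The documents do not support that. Removal needs a treatment-related Grade 4 platelet event and no recovery to Grade 1 within 4 weeks.

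**Conclusion.** The inconsistency within 8.3 is established from the text alone and needs no assumption about CTCAE. The mismatch with 3.17 rests on one assumption, that Grade 1 begins above 30,000/mm³. How far it reaches depends on the true bound: only entrants at 30,000–49,999 with marrow of 50% or more if the bound is 50,000, and also entrants at 50,000–74,999 if it is 75,000.

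Read literally, a patient from that group who has a treatment-related Grade 4 event and returns only to baseline must leave protocol treatment at 4 weeks, strictly so in the first combination cycle. A response not yet confirmed may then be lost.

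The number of such patients cannot be derived. A reader might assume that 10–20% of 34 patients enter below 75,000/mm³ and take 0.10 × 34 = 3.4 to 0.20 × 34 = 6.8 as the number harmed. That counts an assumed group of entrants, not patients with the event, not patients who fail to recover, and not lost responses. No effect on power or on the cut-off of 26 of 34 should be claimed from it.

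The point should be corrected because the contradiction is plain and the correction is small. Which threshold is clinically right is outside this review.

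**What to change.** Reconcile these places in one amendment to the wording: the Grade 4 platelet row of 8.3, its recurrence bullet, the closing paragraph of 8.3, the 28-day limit in 8.1f, the Phase I rule in 7.31, the platelet entry in 8.5, and the platelet limits in 3.17. The text should state:

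- which rule governs restart and which governs removal;
- whether a first event and a recurrence are meant to differ;
- whether the closing paragraph applies to rows that have a removal rule of their own;
- how a patient whose eligible baseline is worse than Grade 1 is handled.

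If the difference between lenalidomide and ibrutinib is intended, a sentence saying so is enough. The sponsor's clinicians choose the threshold. The cost is protocol wording only, with no new tests and no change to the sample size.

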### 8.0 Dosage Modification Based on Adverse Events

Strictly follow the modifications in this table for the first cycle of combination treatment with ibrutinib, lenalidomide and dexamethasone, until individual treatment tolerance can be ascertained (**not including the treatment period where MTD of the combination is being determined as per Section 7.31**). Thereafter, these modifications should be regarded as guidelines to produce mild-to-moderate, but not debilitating, side effects. Reductions apply to treatment given in the preceding cycle and are based on adverse events observed since the prior dose.

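### The Section 8.3 lenalidomide rule for Grade 4 neutropenia contradicts itself when the count recovers to exactly Grade 2

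*Combined protocol and SAP*

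**What the plan says.** The Grade 4 neutropenia row of the lenalidomide table in Section 8.3 has three sentences that depend on a recovery level.

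- Omission: "Omit dose until AE has resolved to Grade 1 or better".
- Restart: once the neutropenia is at most "Grade 2, resume dose at one level lower".
- Removal: if, with lenalidomide omitted, the event is not back to at most "Grade 1 within 4 weeks, then the patient must be removed from protocol treatment and proceed to Event Monitoring".

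The Grade 4 anemia row just below has the same structure but a single level. It reads "Omit dose until AE has resolved to Grade 2 or better", restarts at Grade 2 or better, and removes the patient if the event is not back to at most "Grade 2 within 4 weeks, then the patient must be removed from protocol treatment and proceed to Event Monitoring".

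The sentence that closes Section 8.3 covers lenalidomide toxicities in general. If the toxicity does not return to at most "Grade 2 within 28 days, the patient must be removed from protocol treatment and proceed to Event Monitoring".

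Section 8.0 sets how binding the tables are: "Strictly follow the modifications in this table for the first cycle of combination treatment with ibrutinib, lenalidomide and dexamethasone", leaving out the period in which the Phase I MTD is being determined. It continues: "Thereafter, these modifications should be regarded as guidelines to produce mild-to-moderate, but not debilitating, side effects".

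**The concern.** A dosing rule should give one answer at each blood count. Here, recovery to Grade 2 satisfies the restart sentence but not the omission sentence, so a site is told both to give and to withhold lenalidomide. If the count is still Grade 2 at 4 weeks, the row also requires removal of a patient whom its restart sentence would have on a reduced dose.

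Two sites could follow the row in good faith and treat the same patient differently. One patient would continue on 20 mg. The other would go without lenalidomide for 4 weeks and then leave all protocol treatment. Under Section 16.411 a removed patient who is eligible and has begun treatment remains in the response denominator, so a response that would have come after removal is lost.

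**Working it through.** **Step 1: the row at each recovery grade.** No stated figure has to be reproduced; the check is logical.

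| Recovery | Omission sentence | Restart sentence | Removal sentence at 4 weeks | Result |
|---|---|---|---|---|
| Grade 0-1 | omission ends | resume one level lower | not triggered | consistent |
| Grade 2, before 4 weeks | keep omitting | resume one level lower | not yet due | conflict |
| Grade 2, at 4 weeks | keep omitting | resume one level lower | remove | conflict |
| Grade 3-4 | keep omitting | not triggered | remove | consistent |

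The contradiction is confined to exactly Grade 2.

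**Step 2: search for a precedence rule.** Section 8.1(b) ranks dose reductions when there are several toxicities, not recovery levels within one. Sections 8.1(f) and 13.3 limit an omission to 28 days but name no grade. Section 8.5 governs ibrutinib. The closing sentence of 8.3 requires removal when Grade 2 is not reached, and says nothing on whether a row may be stricter. None of these settles the point.

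**Step 3: which part falls in the strict period.** Under Section 7.12, Phase II lenalidomide starts in Cycle 2, which is therefore the first combination cycle. Numbering days from the start of treatment:

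- Cycle 2 is Days 29-56, with lenalidomide on Days 29-49.
- Cycle 3 is Days 57-84, with lenalidomide on Days 57-77.

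Recovery to Grade 2 can occur before Day 56, so the withhold-or-restart conflict can arise in the strict period. If omission begins as early as Day 30, four weeks is 30 + 28 = Day 58, after Cycle 2 has ended. The removal point therefore falls in the guideline period, although the row still words removal as mandatory.

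**Step 4: doses that separate the two readings.** Assume the 4 weeks run from the day Grade 4 is found and the count stays at Grade 2 once it gets there. The omission sentence then gives 0 doses before the 4-week point. The restart sentence gives:

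| Grade 4 found | Grade 2 reached | 4-week point | Cycle 2 doses | Cycle 3 doses | Total |
|---|---|---|---|---|---|
| Day 36 | Day 43 | Day 64 | Days 43-49: 7 | Days 57-63: 7 | 14 |
| Day 40 | Day 47 | Day 68 | Days 47-49: 3 | Days 57-67: 11 | 14 |
| Day 43 | Day 50 | Day 71 | 0 | Days 57-70: 14 | 14 |
| Day 40 | Day 54 | Day 68 | 0 | Days 57-67: 11 | 11 |
| Day 40 | Day 61 | Day 68 | 0 | Days 61-67: 7 | 7 |
| Day 40 | Day 68 | Day 68 | 0 | 0 | 0 |
| Day 54 | Day 61 | Day 82 | 0 | Days 61-77: 17 | 17 |

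The range over these cases is 0 to 17 doses. Only the first two cases have any doses in the strict period (7 and 3).

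**Step 5: the largest effect on the endpoint.** One affected patient can change at most one response among the 34 evaluable patients: 1/34 = 2.9 percentage points. The change is zero if the patient has already responded or never would. A response already seen can still be confirmed, because Table 11.5, footnote a, accepts consecutive assessments at any time before new therapy.

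**The case against.** The strongest defence is that the practical reach is small. Beyond the first combination cycle the tables are guidelines, the removal point always falls there, the Phase I MTD-determination period is outside the strict rule, and Section 9.7 allows growth factors. All of that stands, and it limits the weight of the point. It does not tell a site what to do at Grade 2 during the strict cycle.

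One could also read the restart sentence as applying only after Grade 1 has been reached. Its Grade 2 level would then have no function, and nothing in the row directs that reading.

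A second objection concerns the intended level, and it largely stands. A reader might infer that Grade 2 was plainly meant. The restart sentence, the anemia row, the febrile neutropenia row and the closing sentence point that way. But the row's other two sentences say Grade 1. So do Section 7.31, for recovery from a Phase I DLT, and the Section 8.5 ibrutinib row for prolonged Grade 4 neutropenia; both of these also accept baseline. The entry floor of 1,000 neutrophils/mm3 in Section 3.17 does not decide it: the CTCAE cut-offs are not in the documents, and a count acceptable before treatment need not be safe for re-exposure after drug-related Grade 4 neutropenia. The choice is clinical and belongs to the sponsor.

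A reader might also take the closing sentence as a further direct contradiction. It is not: requiring removal when Grade 2 is not reached does not forbid a row from removing at a stricter level. It only adds doubt about which level was intended.

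**Conclusion.** The row is wrong as written: at exactly Grade 2 it both withholds and restarts lenalidomide and, at 4 weeks, both treats and removes, with no rule of precedence. This is a minor internal inconsistency in a dosing rule.

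A reader might infer a loss of power or a biased response rate. The documents do not support that. They do not give the frequency of Grade 4 neutropenia that stalls at Grade 2, and no sample size, error rate or decision boundary depends on this row. A reader might also take 14 doses as the general difference between the readings. That figure holds for three cases with recovery 7 days after onset; across all the cases worked the range is 0 to 17, and most of the doses fall in the guideline period. These counts rest on the Phase II calendar and on a count that stays at Grade 2 until the 4-week point.

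**What to change.** Use one recovery level for omission, restart and removal in this row.

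**Default, Grade 2.** *Omit until Grade 2 or better, then resume one level lower; if not Grade 2 or better within 28 days, remove from protocol treatment.* This agrees with the row's restart sentence, the anemia row and the closing sentence of Section 8.3. Its downside is that reduced-dose lenalidomide restarts at a lower neutrophil count than two of the row's sentences now allow.

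**Alternative, Grade 1.** If the sponsor prefers the stricter level, in line with Sections 7.31 and 8.5, change the restart sentence to *Grade 1 or better, or baseline*. Add the same baseline alternative to the omission and removal sentences, and add *unless the row states a stricter level* to the closing sentence.

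In either case, state that Section 8.5 continues to govern ibrutinib when the neutropenia is attributed to it. Check the platelet row in the same edit: it also has two restart levels, Grade 1 and, after recurrence, a count of 30,000/mm3 or more.

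The cost is a few lines of wording. No visits, tests or patients are added.

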**ALERT:** **ADR reporting may be required for some adverse events (See Section 10)**

#### 8.1 General Considerations:

- a) Missed doses are to be omitted rather than made up, unless the dose of one of the study drugs was forgotten and remembered on the same day, in which case the dose can be taken that day. Any doses missed on a particular day are not to be made up the next day.

Doses that are considered to be vomited are not to be made up and a mention about the time of dose and time of vomiting episode should be made in the pill diary.

- b) If multiple toxicities are experienced, dose modifications will be based on the toxicity requiring the largest dose reduction.
- c) Reductions are based on the dose given in the preceding cycle and are based on toxicities with an attribution of possible, probable, or definite that were observed since the prior toxicity evaluation.
- d) If either ibrutinib or lenalidomide must be permanently discontinued, the patient will be removed from the protocol therapy.
- e) If a drug is omitted due to specific adverse events and the patient is on combination therapy, the other agents, considered unrelated to the adverse event may be continued.
- f) A dose omission of >28 days for ibrutinib or lenalidomide is not allowed. If a patient cannot be administered a dose for >28 days due to adverse events or any other reason, the patient should be removed from the study treatment and go to event monitoring.
- g) Patients will be removed from the study if we are unable to manage the adverse events they experience, and it is therefore necessary to permanently discontinue ibrutinib or lenalidomide. These events are listed in the tables in Section 8.3 and 8.5.

8.2 Dose Reductions for Phase I cycles 2 and beyond and Phase II portion (based on Adverse Events in Tables below):

8.21 The following recommended dose modifications will be utilized for ibrutinib, lenalidomide and/or dexamethasone separately as per the best judgment of which drug was most likely to have caused the toxicity:

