**Rare known potential toxicities, <1% (Limited to important or life-threatening):**

Angioedema, Stevens-Johnson Syndrome and Toxic Epidermal Necrolysis

Tumor Lysis Syndrome, Graft vs. Host Disease, rhabdomyolysis, Kidney damage which may require dialysis

15.28 **Drug procurement:** As a requirement of the REMS program, access to Lenalidomide is restricted. Lenalidomide is approved for marketing only under a FDA approved, restricted distribution program called REVCLIMID REMS ([www.REVCLIMIDREMS.com](http://www.REVCLIMIDREMS.com)) formerly known as the RevAssist program. Physicians, pharmacies, and patients must be registered; a maximum 28-day supply may be dispensed; a new prescription is required each time it is filled; pregnancy testing is required for females of childbearing potential.

15.29 **Nursing Guidelines:**

- Myelosuppression is dose-dependent and reversible with treatment interruption and/or dose reduction. Monitor CBC w/diff regularly. Instruct patient to report any unusual bruising or bleeding (thrombocytopenia); signs and symptoms of infection (neutropenia); and energy conserving lifestyle (anemia).
- Lenalidomide can have thrombotic adverse events (i.e DVT and PE). Instruct patient to report any limb swelling or pain, and to seek medical attention for shortness of breath or chest pain.
- Because of the potential for birth defects patients should be instructed in effective methods of birth control. Female patients should use 2 forms of birth control during treatment and for 4 weeks after discontinuing therapy. Males must be instructed to use a latex condom during any sexual contact with a woman of child bearing potential (even if they have had a vasectomy), because it is unknown if lenalidomide is present in semen.
- Patients may experience pruritus, rash and dry skin. Because of the rare risk of Steven's Johnson Syndrome, patients should immediately report any rash to their provider.
- Drug may cause hyperglycemia. Patients with diabetes or impaired fasting glucose may need to have their glucose levels monitored more closely.
- Gastrointestinal side effects (diarrhea, constipation, nausea, dyspepsia, anorexia, etc) are commonly seen. Manage patient symptomatically and monitor for effectiveness.

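### Table 8.3 has no row for Stevens-Johnson syndrome, toxic epidermal necrolysis or Grade 4 blistering rash, so a recovered lenalidomide-related case defaults to a lower-dose restart

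*Combined protocol and SAP*

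**What the plan says.** Section 8.3 sets the lenalidomide actions. It has four skin rows: erythema multiforme Grade 3 or higher, skin ulceration Grade 2 or higher, and non-blistering rash at Grade 3 and at Grade 4. The last of these, "Other: Non-blistering rash Grade 4", ends study treatment.

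The closing row, Other AEs, covers a "Non-hematologic AE assessed as related to lenalidomide" of Grade 3 or higher, with no upper grade limit. The drug is omitted and the event followed at least weekly. Once it is Grade 2 or better, the site is to "implement one dose reduction step and continue therapy (per Table 8.2"). A note under the table sets a limit: if the toxicity has not come back to Grade 2 or better "within 28 days, the patient must be removed from protocol treatment and proceed to Event Monitoring".

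Section 15.27 has a group of rare lenalidomide toxicities marked "Limited to important or life-threatening", which opens with "Angioedema, Stevens-Johnson Syndrome and Toxic Epidermal Necrolysis". Section 15.29 adds: "Because of the rare risk of Steven's Johnson Syndrome, patients should immediately report any rash to their provider".

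Section 8.0 makes the dose tables strict for the first cycle of combination treatment, outside the Phase I MTD period, and a guideline after that.

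**The concern.** The protocol recognises SJS and TEN as serious lenalidomide risks and asks patients to report rash at once because of SJS, but it writes no dosing action for either. Both rash rows are confined to non-blistering rash, so a blistering rash is excluded by their own wording. What remains is a general row whose default after recovery is to resume the drug.

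Two Grade 4 rashes therefore get opposite defaults: the non-blistering one ends treatment, and the blistering one may resume at a lower dose. No reason is given. What is at stake is the safety of an individual patient, not the inference from the trial.

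**Working it through.** No figure in the plan needs reproducing. The check is to trace each event through the rules.

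**1. Which row applies (Section 8.3, lenalidomide-related events)**

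| Event | Row | Default |
|---|---|---|
| Erythema multiforme, Grade 3 or higher | Own row | Ends treatment |
| Skin ulceration, Grade 2 or higher | Own row | Ends treatment |
| Non-blistering rash, Grade 3 | Own row | Omit, then continue at Grade 2 or better; no reduction stated |
| Non-blistering rash, Grade 4 | Own row | Ends treatment |
| Blistering rash, Grade 4 | Other AEs | Omit, then one level lower at Grade 2 or better |
| SJS or TEN, Grade 3 or higher | Other AEs | Omit, then one level lower at Grade 2 or better |

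Of the 4 existing skin rows, 3 end treatment and 0 name SJS, TEN or blistering rash.

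**2. Which cases reach the restart default.** All of these must hold: the event is attributed to lenalidomide; it is Grade 3 or higher; it is not also recorded as ulceration of Grade 2 or higher or erythema multiforme of Grade 3 or higher; and it is back to Grade 2 or better within 28 days. A case recorded instead as an allergic reaction of Grade 2-3 also leads to a restart, 5 mg lower, once it is Grade 1 or better.

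**3. Restart dose.** One step down in Section 8.221 takes a patient on 25 mg to 20 mg. This does not describe patients with creatinine clearance of 30-60 ml/min, who start at 10 mg under Table 8.32 and lie outside that ladder.

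**4. How binding the default is.**
- Phase I: the first combination cycle is Cycle 1, the MTD period, which Section 8.0 excludes. Section 7.31 governs there. It lets a patient with a DLT restart at the next lower level after recovery to Grade 1 or baseline, with no exception for these reactions.
- Phase II: lenalidomide starts in Cycle 2 (Section 7.12), so strict use covers that one cycle. Lenalidomide is taken on days 1-21, so a restart inside the strict window needs both onset and recovery within 21 dosing days. A later restart falls where the table is a guideline.

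**5. Ibrutinib.** Section 15.17 lists SJS as a rare ibrutinib toxicity. The Other row of Section 8.5 (Grade 4, or unmanageable Grade 3) allows the same dose again after a first event that recovers to Grade 1 or baseline. Section 8.1(d) limits the effect: "If either ibrutinib or lenalidomide must be permanently discontinued, the patient will be removed from the protocol therapy". The 8.5 row therefore matters mainly in Phase II Cycle 1, before lenalidomide is given, and for cases attributed to ibrutinib alone.

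**6. Frequency.** Section 15.27 puts SJS and TEN each below 1%. With 34 evaluable Phase II patients (Section 16.12), the expected number of each is below 34 × 0.01 = 0.34 over all cycles. The number reaching the restart default is smaller still. The documents give no figure for that share, so none is computed.

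**The case against.** The strongest reply is that other rules already protect the patient. Section 13.3 lets the investigator withdraw a patient for an adverse event or in the patient's best interests, in any cycle. Section 8.1(b) applies the largest reduction when several toxicities coincide, so ulceration or erythema multiforme at the stated grades would end treatment. The 28-day limit removes slow recoveries. Related Grade 4 or higher non-hematologic events count toward the stopping rules of Section 16.52, and serious Grade 3-5 events go to the sponsor within 24 hours under Section 10.41. All of this stands, and it makes an unnoticed rechallenge unlikely. But the investigator exits apply equally to erythema multiforme and anaphylaxis, for which explicit stops were still written. The reporting and stopping rules act on accrual and oversight, not on the individual's dose.

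A second reply is that tumor lysis syndrome, rhabdomyolysis and kidney damage are on the same list in Section 15.27 and also have no row in 8.3. That is right: being listed does not by itself show a gap. The case rests on the contrast with the neighbouring skin rows.

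Two stronger readings are tempting. A reader might infer that sites are obliged to rechallenge after SJS or TEN; the Section 13.3 exits rule that out. A reader might also infer that Section 8.1(g), which removes patients whose events cannot be managed, gives no cover because it refers to the tables in 8.3 and 8.5 and neither names these reactions. That is strained: its test is whether the event can be managed, and the tables list events by category as well as by name. What can be said is only that 8.1(g) does not clearly reach a case that was managed and recovered.

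**Conclusion.** The point holds as a low-frequency gap that is cheap to close. For two reactions the protocol itself calls important or life-threatening, and for one kind of Grade 4 rash, the written default after recovery is a lower-dose restart, while the matching Grade 4 non-blistering rash ends treatment. That default binds at most within one Phase II cycle and can be overridden.

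The conclusion assumes that such a case would not always be recorded under an existing stop row, and that the below-1% rate carries over to this combination. The documents do not reproduce the CTCAE definitions that would settle the first, and give no combination rate for the second. The recommendation rests on the mismatch between neighbouring rows and the small cost of removing it, not on the expected number of cases.

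Grade 3 blistering rash is not part of the point: there the catch-all, with one step down, is stricter than the Grade 3 non-blistering row. Nor do the documents support reading this as a flaw in the design: sample size, primary endpoint and error rates do not depend on it.

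**What to change.** Add one skin row to Section 8.3 for SJS or TEN of any grade and for blistering rash of Grade 4, with the same action as the existing Grade 4 non-blistering row: permanent stop and transfer to event monitoring. Add one sentence saying that the catch-all rows of 8.3 and 8.5, and the DLT restart provision of 7.31, do not apply to these events. Without the reference to 7.31, Phase I Cycle 1 would keep its restart route. The 8.5 part is needed mainly for Phase II Cycle 1 and for cases attributed to ibrutinib alone. Leave the action for Grade 3 blistering rash to the sponsor's clinicians.

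The cost is a row and a sentence in the next amendment, with no change to sample size or analysis. The downside is that a rare patient who might have tolerated rechallenge would leave treatment.
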